### **10.4** Serious Adverse Events

An adverse event is reported as a "Serious Adverse Event" if it meets any the following criteria (as per ICH GCP Guidelines):

- Results in death
- Is life threatening

- Results in persistent or significant disability/incapacity.
- Requires in-patient hospitalization or prolongs existing hospitalization.
- Is a congenital anomaly/birth defect or spontaneous abortion.
- Any other important medical condition that requires medical or surgical intervention to prevent permanent impairment of a body function or structure.

Serious Adverse Events (SAEs) should be reported to IAVI within 24 hours of the CRC becoming aware of the event. All SAEs should be reported using the designated SAE Report Form and sent to the sponsor according to SAE Reporting Guidelines (see SOM).

To discuss Investigational Product related SAEs or any urgent medical questions related to the SAE, the CRC investigator should contact one of the IAVI medical monitors directly (see the Contact List).

The IAVI SAE Report Form should be completed with all the available information at the time of reporting. The minimum data required in reporting an SAE are the volunteer identification number, date of birth, gender, event description (in as much detail as is known at the time), onset date of event (if available), reason event is classified as Serious, reporting source (name of principal investigator or designee), relationship assessment to the Investigational Product by the investigator.

The Principal Investigator or designee is required to write a detailed written report with follow up until resolution or until it is judged by the principal investigator or designee to have stabilized.

The Principal Investigator or designee must notify the local IRB/IEC of all SAEs as appropriate. In case of Investigational Product related SAEs, the sponsor will ensure the local regulatory authorities are notified as well as the Safety Review Board (SRB), and other research centres where the same Investigational Product is being tested.

More details on SAE definitions and reporting requirements are provided in the SAE Reporting Guidelines (see SOM).

## 10.5 Clinical Management of Adverse Events

Adverse events (AEs) will be managed by the clinical study team who will assess and treat the volunteer as appropriate, including referral. If any treatment/medical care is required as a result of the harm caused by the Investigational Product or study procedures, this care will be provided free of charge.

If a volunteer has an adverse event and/or abnormal laboratory value that is known at the time of study vaccination(s), the specifications of Section 12.0 will be followed.

Volunteers will be followed until the adverse event resolves or stabilizes or up to the end of the study, whichever comes last. If at the end of the study, an adverse event (including clinically significant lab abnormality) that is considered possibly,

probably or definitely related to the Investigational Product is unresolved, followup will continue until resolution if possible and the volunteer will be referred.

## 10.6 Pregnancy

Although not considered an adverse event, if a female volunteer becomes pregnant during the study, it is the responsibility of the Principal Investigator or designee to report the pregnancy promptly to IAVI using the designated forms. However, serious complications of pregnancy that meet SAE criteria specified in the Section 10.4 of this Protocol (e.g., eclampsia, spontaneous abortion, etc.) should be reported as SAEs. If a female volunteer becomes pregnant during the study, vaccinations will be discontinued and the volunteer followed for safety until the end of pregnancy or study completion, whichever occurs last. Approximately 2-4 weeks after delivery, the baby will be examined by a physician to assess its health status and the results will be reported to IAVI.

## 10.7 Intercurrent HIV Infection

HIV infection cannot be caused by the Investigational Product. If a volunteer is found to be HIV-infected through exposure in the community, study vaccinations must be discontinued and the volunteer followed according to procedures described in Section 12.2.

Intercurrent HIV infection in study volunteers, although not considered an SAE must be reported promptly to IAVI using the designated forms. IAVI will report intercurrent HIV infections using the same procedure as SAE reporting. Serious medical conditions associated with the HIV infection that meet SAE criteria specified in the Section 10.4 of this Protocol (e.g. sepsis, pneumonia, etc.) should be reported as SAEs using the SAE Report Form.

## 10.8 Serious Event Prior to Investigational Product Administration

If a serious event occurs in the period between the volunteer signing the Informed Consent Form and receiving their first study injection, the event will be reported using the SAE form and following the same procedures for SAE reporting as indicated in Section 10.4. The type of event will be indicated by using the relevant checkbox on the SAE form.

11.0

# MANAGEMENT OF HIV ISSUES DURING AND FOLLOWING STUDY

### 11.1 HIV Testing

Volunteers will be tested for HIV-1 and HIV-2 antibodies as indicated in the Schedule of Procedures (Appendices A, B and C) or as needed, if medical or social circumstances arise.

If the routine post-vaccination HIV Antibody test is positive, a predetermined algorithm will be followed to distinguish between an immune response to the vaccine from an HIV infection through exposure in the community.

To prevent unblinding of the volunteer and study staff, results will be reported to the CRC as "HIV-infected" or "Not infected with HIV-1 or HIV-2".

If a volunteer is found to be HIV-infected, a newly drawn blood specimen will be collected for confirmation.

Volunteers who have a positive HIV-antibody test(s) as a result of vaccineinduced HIV antibodies rather than a true HIV infection (false positive HIV test) will have their test result reported as "Not infected with HIV-1 or HIV-2" (to prevent unblinding of volunteer and staff) and will be followed up until the test becomes negative. At the end of the study these volunteers will be informed of the false-positive test result and offered continued follow-up.

Should a volunteer require an HIV test outside the study for personal reasons, it is recommended that the volunteer contact the study staff first. The HIV test can be drawn at the CRC and then processed at an independent laboratory as above. Written evidence of HIV status (HIV-infected or HIV-uninfected) will be provided upon request.

All volunteers will receive HIV risk reduction counselling and pre-HIV-test and post-HIV-test counselling as specified in Section 11.3.2.

## 11.2 Social Discrimination as a Result of an Antibody Response to Vaccine

The aim is to minimize the possibility of social discrimination in volunteers (if any) who develop vaccine-induced HIV antibodies and test positive on a diagnostic HIV antibody test. Appropriate diagnostic HIV testing and certification will be provided both during and after the study as needed. In addition, the CRCs will have the option of offering the volunteer a card stating that he/she participates in a research study.

### 11.3 HIV infection

Volunteers who are found to be HIV infected at screening and volunteers who acquire HIV infection during the study will be provided the following:

## 11.3.1 Counselling

The volunteer will be counselled by the study counsellors. The counselling process will assist the volunteer with the following issues:

- Psychological and social implications of HIV infection
- Who to inform and what to say
- Implications for sexual partners
- Implications for child-bearing
- Avoidance of transmission to others in future

## 11.3.2 Referral for Support and/or Care

Volunteers will be referred to a patient support centre or institution of his/her choice for a full discussion of the clinical aspects of HIV infection. Referral will be made to a designated physician or centre for discussion of options of treatment of HIV-infection.

For those individuals who become HIV infected after enrolment in the study, antiretroviral therapy will be provided when clinically indicated according to accepted treatment guidelines. According to IAVI's Treatment and Care Guidelines, antiretroviral therapy will be provided at no charge for up to 5 years after treatment is initiated, if not available free of charge elsewhere.

Volunteers who acquire HIV infection during the study, despite counselling, will complete the Early Termination visit as detailed in the Schedule of Procedures (Appendices A, B and C) and then be referred to IAVI Protocol H, a separate research protocol for follow-up of HIV infected volunteers with clinical, laboratory and immunology assessments.

HIV-infected pregnant women will be referred for prenatal care and to a program for the Prevention of Mother to Child Transmission (PMTCT). A volunteer who becomes pregnant will be followed according to the timeline as specified in Section 10.6

# 12.0 DISCONTINUATION OF VACCINATIONS AND/OR WITHDRAWAL FROM STUDY

## 12.1 Discontinuation of Vaccinations

Any volunteer discontinuing from further vaccinations or being considered for discontinuation of vaccinations will be discussed with the sponsor. Volunteers will be discontinued from further vaccination for any of the following reasons:

- 1. Pregnancy
- 2. Intercurrent HIV Infection
- 3. Use of systemic corticosteroids, immunosuppressive, antiviral, anticancer, antituberculosis or other medications considered significant by the investigator
- 4. A disease or condition or an adverse event that may develop, regardless of relationship to the Investigational Product, if the principal investigator or designee is of the opinion that further study vaccinations will jeopardize the safety of the volunteer
- 5. Any of the following current abnormal laboratory parameters which are known at the time of vaccination:

Haematology

- Haemoglobin <9.0 g/dL or <1.40 mmol/L
- Absolute Neutrophil Count (ANC): < 1000/mm3 or < 1.0 x  $10^{9}$ /L
- Absolute Lymphocyte Count (ALC):  $\leq$  500/mm3 or  $\leq$  0.5 x 10^9/L
- Platelets:  $\leq 90,000 \geq 550,000/\text{mm3} \text{ or } \leq 90 \times 10^9 \geq 550 \times 10^9/\text{L}$

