- 10. Any of the following abnormal laboratory parameters listed below (laboratory parameters must be consistent with I/E criteria prior to each vaccination):
  - i. Hematology
    - a. Hemoglobin <10.0 g/dL
    - b. Absolute Neutrophil Count (ANC):  $\leq 1000/\text{mm}^3$
    - c. Absolute Lymphocyte Count (ALC):  $\leq$  500/mm^3
    - d. Platelets:  $\leq 90,000/$  mm^3
    - ii. Chemistry
      - a. Creatinine: > 1. 1 x ULN
      - b. AST: >1.25 x ULN
      - c. ALT: >1.25 x ULN
  - iii. Urinalysis: abnormal dipstick confirmed by microscopy
    - a. Protein 2+ or more
    - b. Blood 2+ or more (not due to menses)
    - c. Leukocytes 2+ or more
- 11. Receipt of live-attenuated vaccine within the previous 60 days (live attenuated flu vaccine within 14 days) or planned receipt within 60 days after vaccination with Investigational Product; or receipt of other vaccine (e.g. pneumococcal), allergy treatment with antigen injections or tuberculin skin test within the previous 14 days or planned receipt within 14 days after vaccination with Investigational Product
- 12. Receipt of blood transfusion or blood-derived products within the previous 6 months
- 13. Participation in another clinical trial of an Investigational Product currently, within the previous 3 months or expected participation during this study
- 14. Prior receipt of another investigational HIV vaccine candidate (note: receipt of an HIV vaccine placebo will not exclude a volunteer from participation if documentation is available and the IAVI Medical Monitor gives approval)
- 15. History of severe local or systemic reactogenicity to vaccines (e.g.

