## 6.2 Vaccination Visit

Prior to the vaccination, study staff will:

- Answer any questions about the study
- Review the Informed Consent Document with volunteers
- Review screening safety laboratory data
- Conduct HIV risk assessment
- Conduct HIV risk reduction counselling
- Conduct pre- and post-HIV test counselling
- Conduct family planning counselling
- Review interim medical history
- Collect concomitant medication information
- Perform a symptom-directed physical examination and any further examination indicated by history or observation
- Record vital signs (pulse, respiratory rate, blood pressure and temperature)
- Perform baseline local and systemic reactogenicity assessment of the site of vaccination
- Collect specimens for all tests as indicated in the Schedule of Procedures (Appendices A, B and C). Obtain pregnancy test results prior to vaccination.

The volunteer will be assigned an allocation number according to the instructions specified in the Study Operations Manual.

The Investigational Product will be administered as specified in Section 8.4, Administration of Investigational Product.

For the first 20 volunteers enrolled and vaccinated, study staff will closely observe volunteers for at least 4 hours after first vaccination for any acute reactogenicity. For the remaining volunteers, study staff will closely observe volunteers for at least 30 minutes after vaccination. At the end of the observation period study staff will:

- Record vital signs (pulse, respiratory rate, blood pressure and temperature)
- Assess any local and systemic reactogenicity
- Assess any other adverse events.

For subsequent vaccination visits, study staff will perform the same procedures as above with the following exceptions:

- Review the routine safety laboratory parameters (9.1.6) from the previous visit prior to each vaccination. If a volunteer has an abnormal laboratory value that is known at the time of vaccination, follow the specified guidelines (Section 12.0)
- Conduct pre HIV-test counselling if an HIV Test is required (Appendices A, B and C) or provide post-test counselling if the results of a prior HIV test are being provided to the volunteer.
- All volunteers will be observed for at least 30 minutes after vaccination

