Adult and Pediatric, > 7 days	1,000 – 1,300/mm  1.000 x 10  – 1.300 x 10  /L	750 – 999/mm  0.750 x 10  – 0.999 x 10  /L	500 – 749/mm  0.500 x 10  – 0.749 x 10  /L	< 500/mm  < 0.500 x 10  /L
Infant +† , 2 – ≤ 7 days	1,250 – 1,500/mm  1.250 x 10  – 1.500 x 10  /L	1,000 – 1,249/mm  1.000 x 10  – 1.249 x 10  /L	750 – 999/mm  0.750 x 10  – 0.999 x 10  /L	< 750/mm  < 0.750 x 10  /L
Infant •† , ≤1 day	4,000 – 5,000/mm  4.000 x 10  – 5.000 x 10  /L	3,000 – 3,999/mm  3.000 x 10  – 3.999 x10  /L	1,500 – 2,999/mm  1.500 x 10  – 2.999 x 10  /L	< 1,500/mm  < 1.500 x 10  /L
Comment: Parameter changed from "Infant, <1 day" to "Infant, ≤1 day"				
Fibrinogen, decreased	100 – 200 mg/dL 1 .00 – 2.00 g/L OR 0.75 – 0.99 x LLN	75 – 99 mg/dL 0.75 – 0.99 g/L OR 0.50 – 0.74 x LLN	50 – 74 mg/dL 0.50 – 0.74 g/L OR 0.25 – 0.49 x LLN	< 50 mg/dL < 0.50 g/L OR < 0.25 x LLN OR Associated with gross bleeding

LABORATORY					
PARAMETER	GRADE 1 MILD	GRADE 2 MODERATE	GRADE 3 SEVERE	GRADE 4 POTENTIALLY LIFE-THREATENING	
Hemoglobin (Hgb)			•	•	
Comment: The Hgb value changed from 0.155 to 0.62 method with a conversion f for that lab.	206 (the most commonly	used conversion factor).	For grading Hgb results	, obtained by an analytic	
Adult and Pediatric ≥ 57 days (HIV POSITIVE ONLY)	8.5 – 10.0 g/dL 5.24 – 6.23 mmol/L	7.5 – 8.4 g/dL 4.62–5.23 mmol/L	6.50 – 7.4 g/dL 4.03–4.61 mmol/L	< 6.5 g/dL < 4.03 mmol/L	
Adult and Pediatric ≥ 57 days (HIV NEGATIVE ONLY)	10.0 – 10.9 g/dL 6.18 – 6.79 mmol/L OR Any decrease 2.5 – 3.4 g/dL 1.58 – 2.13 mmol/L	9.0 – 9.9 g/dL 5.55 - 6.17 mmol/L OR Any decrease 3.5 – 4.4 g/dL 2.14 – 2.78 mmol/L	7.0 – 8.9 g/dL 4.34 - 5.54 mmol/L OR Any decrease ≥ 4.5 g/dL > 2.79 mmol/L	< 7.0 g/dL < 4.34 mmol/L	
Comment: The decrease		ine			
Infant +† , 36 – 56 days (HIV POSITIVE OR NEGATIVE )	8.5 – 9.4 g/dL 5.24 – 5.86 mmol/L	7.0 – 8.4 g/dL 4.31 – 5.23 mmol/L	6.0 – 6.9 g/dL 3.72 – 4.30 mmol/L	< 6.00 g/dL < 3.72 mmol/L	

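### The mmol/L half of the haemoglobin stopping limit in Protocol section 12.1 is about four times too low on the scale used in Appendix D

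*Protocol*

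**What the plan says.** Section 12.1 (Discontinuation of Vaccinations), item 5, lists laboratory values that end vaccination if known at the time of dosing. The haemoglobin entry is "Haemoglobin <9.0 g/dL or <1.40 mmol/L". The section states no conversion factor.

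Section 6.2 (Vaccination Visit) makes this an operative limit at the second and third doses: "If a volunteer has an abnormal laboratory value that is known at the time of vaccination, follow the specified guidelines (Section 12.0"). Section 10.5 points to the same place.

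Appendix D, the severity grading table, carries a comment on haemoglobin units: "The Hgb value changed from 0.155 to 0.62". The sentence is broken in the copy reviewed, but the remaining digits make the new factor 0.6206, and the comment describes it as the one in most common use. For HIV-negative adults the lower end of Grade 2 is printed as part of "9.0 – 9.9 g/dL 5.55 - 6.17 mmol/L", and Grade 4 as "< 7.0 g/dL < 4.34 mmol/L".

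Exclusion criterion 10 in section 5.2.4 gives a separate limit, "Hemoglobin <10.0 g/dL", with no SI equivalent, and adds that "laboratory parameters must be consistent with I/E criteria prior to each vaccination".

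**The concern.** One protocol gives two SI values for 9.0 g/dL: 1.40 mmol/L in section 12.1 and 5.55 mmol/L in Appendix D. The pair in section 12.1 looks like a leftover from the older conversion factor.

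This figure decides whether a volunteer receives another dose. Section 7.6 has the safety tests run at the research centres' own laboratories, so reporting units may be set locally. An SI limit is of use only to someone holding a result in mmol/L. If that result is on the Appendix D scale, the SI half would not act until haemoglobin had fallen far below the Grade 4 boundary.

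**Working it through.** **Inputs**
- Stopping limit: 9.0 g/dL and 1.40 mmol/L (section 12.1, item 5).
- Old and new factors: 0.155 and 0.6206 mmol/L per g/dL (Appendix D, haemoglobin comment).
- Appendix D pairs for HIV-negative adults: 10.0 g/dL with 6.18, 9.0 with 5.55, and 7.0 with 4.34 mmol/L. The row for infants up to 21 days pairs 9.0 with 5.59.

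**Formula:** mmol/L = g/dL x factor.

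**1. Reproducing the protocol's figure.** 9.0 x 0.155 = 1.395, which rounds to 1.40. In reverse, 1.40 / 0.155 = 9.03 g/dL. So 1.40 is the old-factor conversion.

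**2. Confirming the Appendix D scale without the broken comment.** The ratio of each printed pair is:
- 6.18 / 10.0 = 0.618
- 5.55 / 9.0 = 0.617
- 4.34 / 7.0 = 0.620
- 5.59 / 9.0 = 0.621

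All lie close to 0.6206 and none is near 0.155.

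**3. The limit on the Appendix D scale.** 9.0 x 0.6206 = 5.585. The adult row prints 5.55, a small rounding difference within Appendix D.

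**4. What 1.40 mmol/L means on that scale.** 1.40 / 0.6206 = 2.26 g/dL, against an intended 9.0. The Grade 4 boundary is 4.34 / 0.6206 = 6.99 g/dL.

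**5. Size of the error.** 5.55 / 1.40 = 3.96. The ratio of the two factors is 0.6206 / 0.155 = 4.00.

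**6. The rest of the haematology list.** These SI limits convert correctly: 1000/mm³ = 1.0 x 10⁹/L, 500/mm³ = 0.5 x 10⁹/L, 90,000/mm³ = 90 x 10⁹/L, and 550,000/mm³ = 550 x 10⁹/L. Haemoglobin is the only entry out of line.

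**7. Effect by reporting basis.** The protocol does not state the centres' units, so all three cases are shown.

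| Centre reports | Effect of the 1.40 figure |
|---|---|
| g/dL | None; the 9.0 g/dL half applies |
| mmol/L with factor 0.155 | None; 1.40 corresponds to 9.0 g/dL |
| mmol/L on the Appendix D scale, reading only the SI half | Acts at 2.26 g/dL; misses 1.40 to 5.54 mmol/L (about 2.3 to 8.9 g/dL) |

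The missed range in the last case contains all of Appendix D Grade 3 (4.34 to 5.54 mmol/L) and Grade 4 down to 1.40 mmol/L.

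**The case against.** The strongest defence is that the limit is coherent on its own terms: under 0.155, 9.0 g/dL and 1.40 mmol/L are the same value. Appendix D calls the newer factor the commoner one, not the only valid one, and its damaged comment appears to allow for laboratories using another factor. Item 5 does not cite Appendix D, whereas item 7 does. On this view the fault is a difference of unit scale between two sections.

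The rule also has several safeguards. Any value below 9.0 g/dL triggers it whatever the SI figure says. Criterion 10 sets a stricter limit before each dose. Item 4 lets the investigator stop on safety grounds, and discontinuations are discussed with the sponsor. A reader working in mmol/L might also find 1.40 implausible beside the Appendix D limits.

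The safeguards stand, and they are why the consequence is small. They do not make the figure right. Section 12.1 names no factor, and the protocol's only other adult SI limits for haemoglobin are on a scale four times larger. Criterion 10 has no SI value, so it cannot settle which reading is meant.

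The objection that 5.55 is itself slightly off is correct: 5.55 / 0.6206 = 8.94 g/dL. That gap is trivial, and 5.55 is the value the protocol already prints for adults.

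**Conclusion.** The concern holds. The SI half of the haemoglobin stopping limit rests on a factor that the protocol's own grading table says was replaced. On the grading table's scale it is about four-fold too low, equivalent to about 2.3 g/dL where 9.0 g/dL is intended. The g/dL half is not in question.

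Whether anyone would be affected depends on an assumption the protocol does not settle: that some centre reports mmol/L on the Appendix D scale and applies only the SI half. Otherwise there is no effect. Laboratory grading uses Appendix D, so no endpoint, sample size or analysis is touched. This is a wrong figure in a safety threshold with low practical consequence, and it should be corrected.

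**What to change.** In section 12.1, item 5, either replace 1.40 with 5.55 mmol/L, to match the Appendix D row for HIV-negative adults, or delete the SI figure and keep 9.0 g/dL alone. Deletion also avoids the small rounding gap between 5.55 and 5.585. The clinical team should confirm the intended limit. The cost is one number in one line.

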## Chemistry

- Creatinine: >1.4 x ULN
- AST: >3.0 x ULN
- ALT: >3.0 x ULN

Urinalysis: Dipstick 3+ confirmed by microscopy for

- Protein
- Blood (not due to menses)
- Leukocytes
- 6. Receipt of live attenuated vaccine within the previous 60 days (live attenuated flu vaccine within 14 days) or planned receipt within 60 days after vaccination with Investigational Product or receipt of other vaccine within the previous 14 days or planned receipt within 14 days after vaccination with Investigational Product
- 7. A Grade 4 local reactogenicity event (as per Appendix D) involving the injected arm
- 8. Anaphylaxis; bronchospasm; laryngeal oedema; convulsions or encephalopathy following study vaccinations.
- 9. Life threatening adverse event following study vaccinations unless not related to the Investigational Product and fully resolved.
- 10. Any immediate hypersensitivity reaction judged to be related to the Investigational Product, if the principal investigator or designee is of the opinion that further study vaccinations will jeopardize the safety of the volunteer
- 11. Volunteer requests to discontinue further vaccination.
- 12. Participating in another clinical study of an Investigational Product

## **12.2** Follow Up After Discontinuation of Further Vaccinations

Volunteers, in whom study vaccinations are discontinued due to adverse events, will be followed until the adverse event resolves or stabilizes or up to the end of the study, whichever comes last. These volunteers will not be replaced.

Follow-up of pregnant volunteers will be done as specified in Section 10.6.

